2.8.4.3 Cumulative incidence of severity grade ≥ 3 infection

Time to first occurrence of infection is defined as time from start of study treatment to the date of first occurrence of an infection of severity grade ≥ 3 , i.e. time in days is calculated as (start date of first occurrence of infection with CTC grade ≥ 3) – (start of study treatment) +1.

The cumulative incidence analysis will consider death or discontinuation from study treatment (due to any reason) without prior infection as competing risks.

In the absence of an event during the on-treatment period, the censoring date applied will be **the earliest** of the following dates:

- data cut-off date
- withdrawal of informed consent date

whereas dates for competing risks are:

- death date
- end date of on-treatment period

Cumulative incidence curves for time to grade ≥ 3 infections as well as summary tables for the number of subjects with event/competing risk/censored and cumulative incidence estimates at 1, 2, 6 months etc. with 95% confidence intervals will be presented overall and for each age group (if sufficient number of patients are available in the age groups) as well as by treatment-naïve vs SR-cGvHD.

2.8.4.4 Acceptability and Palatability assessment

All acceptability and palatability assessment data of all subjects using liquid formulation will be summarized and listed by Age group in the final study report.

2.8.4.5 Development (Growth and sexual maturation)

Growth

Graphical displays of percentile of height and weight over time will be provided for signal detection of impact on growth development. In case of a signal, further analyses may be provided.

In addition, a shift tables for height, weight, and BMI will be provided using following low/normal/high/(low and high) classification to compare baseline to the worst on-treatment value. Low: below the 5th percentile, Normal: between 5th and 95th percentiles, High: above the 95th percentile. Percentiles are based on CDC Growth Charts, derivation is described below.

Height and BMI will be summarized at 6-month intervals, using the standard deviation scores (SDS, also called z-score), velocity and velocity SDS as appropriate. The relevant height and weight values for each 6-month period are defined using time windows, according to [Table 2-1](#). The z-scores will allow identification of potential outliers.

SDS will be calculated using the current formulae provided by the CDC as follows:

$$\text{Calculate } z_{\text{ind}} = \frac{\left(\frac{x}{M}\right)^L - 1}{LS}$$

where:

- X is height in centimeters or BMI in kilograms/m²,
- L, M and S are height or BMI-, sex- and age-specific reference values from the CDC Growth Charts.

The CDC Height-for-age and BMI-for-age L, M and S reference values for males and females are available under <https://www.cdc.gov/growthcharts>. The age category immediately above the patient's exact age should be used. SDS is actually a Z score that measures the distance from the population mean in units of standard deviations. That is, SDS < 0 refers to values lower than the population mean, and for example SDS ≤ -1.645 refers to values in the lowest 5%. The percentile can be derived from the z-score by a normal distribution.

Height velocity is defined as follows:

Height velocity (cm/6-months) = (height in time window k – height in time window $k-1$) \div ([assessment date in time window k – assessment date in time window $k-1$] \div [365.25/2]),

and similarly for weight velocity.

Velocity SDS is calculated as (velocity – mean) / SD, where mean and SD are obtained as the height-, weight-, sex- and age-specific values ([Baumgartner et al 1986](#)), where the age category immediately above the patient's exact age (at the assessment date in time window k) should be used. Velocity SDS will only be calculated for time window k if data also exists for time window $k-1$, since calculating across multiple units of 6 months requires more than one reference value to be taken into account.

All height/length, weight, BMI, standardized scores (percentile and SDS) will be listed.

Sexual maturation

Sexual maturation will be monitored by the Tanner stages. Tanner stage includes two components for boys, namely genitalia stage and pubic hair stage, and two components for girls: breast development stage and pubic hair stage. The overall Tanner stage is derived by the maximum of the two stages (Tanner stage of pubic hair and Tanner stage of genitalia/breast development) from the same assessment.

Tanner stage will only be analyzed among pre-pubescent patients. Therefore, analysis will be based on patients from the Safety Set who were classified as Tanner Stage 4 or lower at the latest assessment prior to the start of study treatment.

It is expected that data will become available during the trial on a proportion of patients as they go through puberty attaining higher levels of the Tanner Stage. The age at which Tanner Stages 2-5 are achieved, and the age at menarche (females), will be displayed graphically and summarized descriptively (if sufficient number of patients are available).

All available sexual maturation data will be included in the figures and listed.

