8.4.3 Tanner staging

Assessments of reproductive development will be performed using the Tanner Staging scale at screening for subjects enrolled in Groups 1, 2 and 3. Tanner staging assessments are not required for subjects enrolled in Group 4. Additional Tanner Staging assessments will be based on the score at screening and subsequent scores:

- Stage 5 = no additional Tanner Staging assessments needed.
- Stage 4 or less = continue Tanner Staging assessments per [Table 8-1](#).

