12.5.2.4 Development (Growth and sexual maturation)

Graphical displays of percentile of height and weight over time will be provided for signal detection of impact on growth development. In case of a signal, the following further analyses may be provided.

Height and Body Mass Index (BMI) will be summarized at 6-month intervals, using the standard deviation scores (SDS, also called z-score), velocity and velocity SDS. SDS will be calculated based on published referenced height and BMI information.

Height/BMI SDS and height/weight velocity SDS will be summarized using descriptive statistics (mean, standard deviation, range) for each time window, as well as by presenting number of patients with SDS values lower/higher than 5th/95th percentiles respectively. All height/BMI SDS, velocity and velocity SDS data will be listed.

Sexual maturation will be monitored by Tanner staging. The age at which Tanner Stages 2 to 5 are achieved by gender will be summarized descriptively. All tanner stage data will be listed.

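### The overall Tanner stage is the higher of two component stages and no component summary is planned, so a delay confined to one component can be masked in the puberty summary

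*SAP*

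**What the plan says.** SAP 2.8.4.5 (Development) sets out the two scores: "Tanner stage includes two components for boys, namely genitalia stage and pubic hair stage, and two components for girls: breast development stage and pubic hair". It reduces them to one: "The overall Tanner stage is derived by the maximum of the two stages", taken from the same assessment.

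The planned output is: "The age at which Tanner Stages 2-5 are achieved, and the age at menarche (females), will be displayed graphically and summarized descriptively", if there are enough patients. The analysis is limited to Safety Set patients "who were classified as Tanner Stage 4 or lower at the latest assessment prior to the start of study treatment". The section closes: "All available sexual maturation data will be included in the figures and listed".

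Protocol 12.5.2.4 plans the same summary, split by sex and without a maximum rule: "The age at which Tanner Stages 2 to 5 are achieved by gender will be summarized descriptively". It also lists all Tanner data. Protocol 8.4.3 ends staging on a single score: "Stage 5 = no additional Tanner Staging assessments needed". Protocol Table 8-1 schedules staging annually after screening.

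Two things are left unsaid. The SAP does not state whether the stage in the age summary and in the analysis set is the overall stage or a component stage. Protocol 8.4.3 does not state which of these Stage 5 refers to.

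**The concern.** The Tanner analysis is there to show whether sexual maturation is disturbed during treatment. Delay is a reasonable direction to worry about, given the growth-retardation risk described in Protocol 4.5, although the documents do not name delayed puberty as the expected harm. If the stage is a maximum, a child counts as having reached a stage when the faster component reaches it, and a slower component can stall without changing the result.

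The overall stage is the only derived variable in this part of the section, and age at stage is the only Tanner summary. It is therefore natural to read the overall stage as feeding both the summary and the Stage 4 or lower restriction. On that reading, a child with pubic hair at Stage 5 and genitalia or breast at Stage 3 or 4 is classed as Stage 5 and excluded, although one component is still developing. If Stage 5 in Protocol 8.4.3 also means the overall stage, staging stops for that child, and the later course of the lagging component is missing from the listings and figures too.

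**Working it through.** The documents give no figure for the Tanner analysis, so there is none to reproduce. The check has two parts.

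**1. Logic, using only the SAP rule.** Let overall stage = max(A, B). Then age at reaching an overall stage = min(age for A, age for B). Lowering A by one stage leaves the maximum unchanged exactly when A was level with or behind B.

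- With A from 2 to 5 and B from 1 to 5 there are 20 pairs, and the overall stage is unchanged in 10.
- Where the components differ by at most one stage there are 11 pairs, and it is unchanged in 7.
- If both ages move later by d, min(a + d, b + d) = min(a, b) + d, so a delay in both components shows in full.

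**2. Size, using assumptions that are not in the documents.** Take the two component ages at a given stage as bivariate normal, each with SD 1.1 years (range 0.9 to 1.3) and correlation 0.7 (range 0.5 to 0.85). Let L be the time by which the affected component normally leads the other, and d its delay.

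- SD of the difference in ages: s = 1.1 × √(2 × (1 − 0.7)) = 0.852 years.
- With one mean at m and the other at 0: E[min] = m·Φ(−m/s) − s·φ(m/s).
- Shift in mean overall age = E[min] at m = d − L, minus E[min] at m = −L.

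Values needed for d = 1:

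- m = 0: −0.852 × 0.3989 = −0.340
- m = 1: 1 × 0.1203 − 0.852 × 0.2004 = −0.050
- m = −1: −0.8797 − 0.1707 = −1.050
- m = 0.5: −0.147
- m = −0.5: −0.647

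| Affected component normally | Shift for a 1-year delay | Over the SD and correlation ranges |
|---|---|---|
| Level (L = 0) | −0.050 − (−0.340) = 0.29 y | 0.19 to 0.35 y |
| 0.5 y ahead | −0.147 − (−0.647) = 0.50 y | 0.50 y throughout |
| 1 y ahead | −0.340 − (−1.050) = 0.71 y | 0.65 to 0.81 y |

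If the affected component is normally behind, less shows. With SD 1 year and correlation 0.3 to 0.9, a component 0.5 years behind shows 3% to 21% of a 1-year delay.

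The 0.29-year shift in the level case does not conflict with part 1. Even when the mean ages are equal, the affected component leads in some children, and a delay in those children does move the minimum.

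**The case against.** **The text does not tie the summary to the overall stage.** The SAP says Tanner Stages 2-5, without the word overall, and the protocol has no maximum rule. This stands, and the point is therefore conditional. But no component-level summary is named, so the wording needs correcting on either reading.

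**The data are not lost.** All sexual maturation data go into figures and listings, and age at menarche is reported separately. With 46 children enrolled (22, 17 and 7 in Groups 1 to 3) and a summary produced only if numbers suffice, figures and listings may be the main readout. A reader might infer that a one-component delay is mostly hidden from the whole puberty analysis. The documents do not support that, because the masking is in the summary. Two limits remain: menarche covers girls only, and the listings may be cut short if staging stops on the overall Stage 5.

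**The size is not fixed.** A reader might also take the level case alone and conclude that 65% to 81% of a 1-year delay is hidden. That range requires equal mean ages for the two components, which the documents do not give. If the affected component normally leads by 0.5 or 1 year, about 50% or 71% of the delay shows.

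**The setting is descriptive.** This is a single-arm study with annual staging and no reference ages specified for the Tanner summary, so no shift is tested. Annual staging would blur component ages just as much. The documents give no reason to expect a delay in only one component. All of this is fair and keeps the matter away from the primary endpoint, but it does not justify discarding component information from the only planned summary.

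**Conclusion.** The concern holds in conditional form. The maximum rule is explicit and no component summary is planned. If, as the section most naturally reads, the overall stage feeds the age summary and the analysis set, a delay in a component that is level with or behind the other does not appear in the summary, and a child with one component complete and the other still developing is left out.

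Under the assumed SD of 1.1 years and correlation of 0.7, a 1-year one-component delay moves the mean overall age by about 0.29, 0.5 or 0.7 years when the affected component is normally level, 0.5 years ahead or 1 year ahead. The documents do not say which case applies, so no single percentage hidden should be quoted. The finding concerns a descriptive safety display. It is worth correcting because the population is children and the change is small.

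**What to change.** - In SAP 2.8.4.5, summarise and plot age at Stages 2-5 separately for pubic hair and for genitalia or breast, by sex.
- Define the analysis set per component: that component at Stage 4 or lower at the last assessment before treatment.
- Keep the overall stage, if wanted, only as a supplementary display, and say where it is used.
- State whether Stage 5 in Protocol 8.4.3 means the overall or the component stage. Flag children whose lagging component was no longer assessed.

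The cost is SAP wording plus one extra table and figure per component. Numbers per stage will be small. If staging stopped on the overall stage, SAP wording cannot recover the missing later assessments, so the flag is needed to show how many children are affected.

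### The age-at-Tanner-stage summary has no number at risk and no censoring rule, so children who never reach a stage during observation do not affect it; the set is also called pre-pubescent although it includes Stages 2 to 4.

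*SAP*

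**What the plan says.** SAP 2.8.4.5 limits the Tanner analysis by label: "Tanner stage will only be analyzed among pre-pubescent patients". The operative rule that follows takes Safety Set patients "who were classified as Tanner Stage 4 or lower at the latest assessment prior to the start of study treatment". The section expects only partial information: "It is expected that data will become available during the trial on a proportion of patients as they go through puberty". The output is then specified as "The age at which Tanner Stages 2-5 are achieved, and the age at menarche (females), will be displayed graphically and summarized descriptively", subject to the condition "if sufficient number of patients are available", with no number given. It closes with "All available sexual maturation data will be included in the figures and listed".

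Protocol 12.5.2.4 has the same analysis split by sex: "The age at which Tanner Stages 2 to 5 are achieved by gender will be summarized descriptively". The SAP sentence does not carry the split over for the Tanner stages.

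Neither document states a number at risk per stage, how a child who has not reached a stage is handled, how a stage already present at entry is handled, or a reference age.

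**The concern.** A descriptive mean or median of age at attainment is conditional on attainment. Children who remain below a stage throughout observation have no value to contribute, and they are the ones a maturation safety analysis most needs to count. Without a number at risk, a small number of attainers cannot be interpreted: it could mean few children were eligible to attain, or that many were and did not.

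Tanner stage is a named part of the secondary safety endpoint (Protocol Table 2-1). Growth, in the same SAP section, gets reference-based scores, velocity scores and shift tables. Puberty gets a summary that stays still under the most serious form of the effect.

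The label adds a smaller problem. A child who enters at Stage 4 passed Stages 2 to 4 at ages the study did not observe, and the plan does not say that such stages are left out of the age summary.

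**Working it through.** The documents give no figure to reproduce for this analysis, so the check asks how the planned statistic behaves.

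**By hand.** Suppose five children reach a stage at 11.0, 11.5, 12.0, 12.5 and 13.0 years. The mean is 60.0/5 = 12.0 and the median is 12.0. Now add five children at risk who never reach it. The mean and median are still 12.0. The proportion attaining falls from 5/5 to 5/10, but that proportion is not planned.

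**By simulation.**

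Inputs from the documents:
- 46 enrolled: 22 aged 12 to under 18, 17 aged 6 to under 12, 7 aged 2 to under 6 (Protocol, Amendment 2 summary).
- Annual Tanner staging (Protocol Table 8-1).
- Follow-up to 3 years from first dose (Protocol 8.2.1).

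Assumptions not in the documents:
- Entry ages uniform within each age group, sexes pooled, no dropout.
- Age at attainment normal, with mean 11.0 and SD 1.1 (early stage) or mean 14.5 and SD 1.2 (late stage).

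A child is at risk if the true attainment age exceeds the entry age. Attainment is recorded at the next annual visit and counts if that visit falls within 3 years. Arrest removes attainment for a random share of those at risk. Delay adds a fixed time for all of them. The Kaplan-Meier (KM) median uses age as the time scale, delayed entry at baseline age and right censoring; it was computed on all 4,000 simulated trials pooled.

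| Scenario | Early: mean age of attainers | Early: number attaining | Early: KM median | Late: mean age of attainers | Late: number attaining | Late: KM median |
|---|---|---|---|---|---|---|
| No effect | 11.54 | 8.4 | 11.5 | 15.06 | 10.1 | 15.0 |
| 30% arrest | 11.55 | 5.9 | 12.1 | 15.06 | 7.2 | 15.6 |
| 50% arrest | 11.55 | 4.1 | 12.7 | 15.05 | 5.1 | 16.3 |
| 1-year delay | 12.55 | 5.7 | 12.8 | 16.02 | 6.7 | 16.3 |
| 2-year delay | 13.54 | 2.9 | 14.0 | 17.01 | 3.1 | 17.8 |
| 3-year delay | none | 0 | none | none | 0 | none |

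A separate run with the early mean set at 11.2 (SD 1.1) agrees: 11.74 years and 8.6 attainers with no effect, 11.73 and 4.3 with 50% arrest, 12.74 and 5.8 with a 1-year delay.

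**Reading the table.** Under arrest the mean moves by at most 0.01 year while the number attaining roughly halves. Under delay within follow-up the mean moves by about the length of the delay. With a delay as long as follow-up there are no new attainers and the summary is empty.

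**What a denominator would show.** With the early mean at 11.2 and an even sex split (assumed), about 11 children per sex are below Stage 2 at entry, or about 22 in all. The proportion attaining is then about 8.6/22 = 39% with no effect and 4.3/22 = 20% with half arrested.

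**The case against.** Several objections have force.

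- A reader might infer that delayed puberty in general goes unseen. It does not: a delay that resolves within follow-up raises the reported age by about its full length.
- A reader might infer that the SAP excludes non-attainers from its outputs. It contains no such rule. Their absence from the mean and median follows from having no censoring rule, and the section puts all maturation data into figures and listings, where a child stuck at one stage can be seen. A falling count of attainers would also show wherever it is printed.
- A reader might infer that baseline age will be entered as the age of attainment for children already in puberty. Nothing says so, and the SAP's reference to data arising during the trial points to transitions on study. The gap is a missing instruction.
- The set label is a naming slip. Membership is explicit, can be programmed, and matches Protocol 8.4.3, which continues staging for Stage 4 or less.
- The growth risk described in Protocol 4.5 concerns bone, and growth has its own analyses. The documents name no puberty signal.
- A full time-to-event analysis would be fragile. With about 11 at risk per sex, the KM median averaged 11.6 years (SD 0.76) with no effect. Under 50% arrest it averaged 12.1 years and could be estimated in only 70% of trials. The shift, 12.1 − 11.6 = 0.5 year, is less than one SD. Treating the annual visit as the attainment date also biases the median upwards (11.5 against an assumed 11.0).

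All of this stands. It narrows the point and limits the remedy, but leaves the core intact: no planned statistic counts the children who were at risk and did not attain.

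**Conclusion.** The point holds in limited form. The planned mean and median are unaffected by children who do not reach a stage during observation, whether from arrest or from delay beyond follow-up. In simulation, 50% arrest about halved the number attaining and moved the mean by no more than 0.01 year. The arrest result does not depend on the particular ages assumed, because those who attain remain a random subset of those who would have attained. It does assume that arrest is unrelated to when a child would have attained. The absolute ages and counts do depend on the assumed distributions, uniform entry ages, pooled sexes and absence of dropout.

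The documents do not support the wider readings that all delay is invisible or that non-progressors vanish from the report. The mislabelled set is a wording fault that leaves membership clear. This is a minor improvement to a descriptive safety output and has no bearing on the primary analysis.

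**What to change.** In SAP 2.8.4.5:

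1. Rename the set as patients not at Stage 5 at baseline.
2. For each of Stages 2 to 5, and for menarche in girls, restrict to children who had not reached it at baseline. Report the number at risk and the number and proportion attaining, by sex as in Protocol 12.5.2.4.
3. State that no attainment age is assigned to a stage already present at baseline.
4. Where numbers allow, with a stated minimum, add an attainment curve on the age scale with delayed entry at baseline age, censoring at the last Tanner assessment, and interval censoring to reflect annual staging. The counts in item 2 are the essential change; the curve is optional.
5. State whether annual stagings from early discontinuation follow-up (Protocol 9.1.1 and Table 8-1) count. SAP 2.1.1 restricts safety tables and figures to the on-treatment period, while SAP 2.8.4.5 promises all available maturation data in the figures.

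The cost is some SAP wording and one extra table or figure, with no new data collection. Intervals will be wide, and without a control arm or reference ages the result can flag slow progression but cannot attribute it to ruxolitinib.

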2.9 Pharmacokinetic endpoints

Analyses of PK data will not be repeated for the final CSR, since no PK samples were collected since interim CSR analyses..

Pharmacokinetic analysis set (PAS) will be used in all pharmacokinetic data analysis and PK summary statistics.

Pharmacokinetic variables:

Ruxolitinib concentration sparse profiles will be summarized by time point. Pharmacokinetic parameters, e.g. AUC0-12h and Cmax and Ctrough, may be determined using Population PK method(s) for ruxolitinib, and methods detailed in an independent analysis plan.

Statistical methods for pharmacokinetic analyses

Ruxolitinib concentrations data will be listed by Age group and formulation. Descriptive summary statistics will be provided by Age group/formulation at each scheduled time point. Summary statistics will include n (number of subjects with non-missing values), mean (arithmetic and geometric), standard deviation (SD), coefficient of variation (CV%) (arithmetic and geometric), median, minimum and maximum. Individual profiles with median by Age group/formulation as well as arithmetic mean with SD and geometric mean ruxolitinib plasma concentration versus time profiles by treatment will be displayed graphically.

Ruxolitinib plasma PK parameters data will be listed by Age group/formulation. Descriptive statistics (n, arithmetic mean, SD, CV% for mean, geometric mean, geometric CV%, median, minimum and maximum) will be provided for all PK parameters by Age group/formulation.

Population PK approach Concentration results from the sparse sampling will be analyzed using nonlinear mixed effects modeling (population PK) or other model-based approaches, as appropriate, and key pharmacokinetic parameters may be derived for the study population from sparse concentration-time data e.g. AUC, Cmax, Ctrough. Details of the analysis method will be developed in an independent PK analysis plan and the population PK analysis will be documented in a separate report.

During modeling of the pharmacokinetics of study treatment, the broad principles outlined in the Food and Drug Administration (FDA) guidance will be followed (Guidance for Industry: Population Pharmacokinetics; fda.gov/cder/guidance/1852fnl.pdf).

Data handling principles

All concentration values below the lower limit of quantitation (LLOQ) are set to zero by the Bioanalyst, and will be displayed in the listings as zero and flagged. LLOQ values will be treated as zero in any calculations of summary statistics, and treated as missing for the

calculation of the geometric means and their CV%. The number of non-zero concentrations will also be reported in the summary statistics.

Missing values for any PK data will not be imputed and will be treated as missing.

